## **Efficacy, Safety, and Costs of 0.25% Timolol Gel in Healing Surgical Open Wounds: A Randomized Trial**

### **Background and Significance**

Healing of a cutaneous defect by second intention is a complex process. Migration of fibroblasts, keratinocytes, and other cell types to the site of defect and their proliferation under stimulation by cytokines and growth factors occur during this process. The role of topical beta-blockers in promoting wound healing is currently emerging in the international literature (1-3).  $\beta$ 2-Adrenergic receptors (B2AR) are the only subtype of beta-adrenoceptors expressed on skin (4-6). They can be found in secretory coil of apocrine glands, keratinocytes, fibroblasts and melanocytes. The distribution of these receptors provides insight on dermatological disorders that may be affected by  $\beta$ -blockers. Keratinocyte migration occurs by the facilitation of chemotaxis, the polarization of cells, and activation of extracellular signal-related kinases essential in the signaling of promigratory pathways. The B2AR activation inhibits keratinocyte migration by activating the serine/threonine phosphatase 2A, which downregulates phosphorylation of extracellular signal-related kinases necessary for migration. Therefore, B2AR antagonists prevent the phosphorylation of phosphatase 2A and have the downstream effect of extracellular signal-related kinase promotion, inducing a promigratory pathway in keratinocytes (4-6). Keratinocyte migration also occurs by galvanotaxis, a phenomenon in which cells migrate in response to electric stimuli. Keratinocytes can be stimulated to migrate with the formation of electrical poles and the application of electrical fields. The B2AR antagonists improve the ability of keratinocytes to respond to such migratory cues, whereas the B2AR agonists decrease keratinocytes' ability to respond, further implicating the use of topical timolol for recalcitrant wounds (4-6). Angiogenesis and dermal fibroblast proliferation are also regulated by B2ARs. The B2AR antagonists have been found to promote angiogenesis in chick chorioallantoic membrane assays and in vivo murine wound models. Dermal fibroblast migration is also increased (by 27%) when exposed to B2AR antagonists, and epidermal differentiation is improved with B2AR antagonists and  $\beta$ 1- and  $\beta$ 2-receptor antagonists (5-10).

## **Specific Aims**

To assess in a randomized fashion the efficacy and safety of topically applied 0.25% timolol gel in promoting wound healing and improve scar cosmesis of surgical open wounds <1.5cm when compared to the standard of care (SOC) by:

1. Evaluating healing in response to treatment with 0.25% topical timolol gel versus SOC in terms of wound surface area reduction of open surgical wound;
2. Evaluating cosmetic outcomes of surgical wounds in terms of blinded physician (4D multidimensional VAS) and patient (Visual Analogue Scale, VAS) assessment at 3 and 6 months follow up;
3. Evaluating patient discomfort during the healing process by means of a patient pain VAS;
4. Determining the side effects associated to 0.25% topical timolol versus SOC; and
5. Determining costs associated to the use of 0.25% topical timolol versus SOC.

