### SOC group:

- 1) Vaseline will be applied to wound bed immediately after surgery before dressing is applied
- 2) Starting the day after surgery: each day, the patient will cleanse the surgical site, apply Vaseline, and re-cover wound with clean dressing
- 3) This daily routine continues for 12 weeks' post-surgery (even if the surgical defect has completely healed in the interim)

Patients will be followed up at 7, 15, and 30 days' post-surgery and then at 3 and 6 months. Standardized pictures will be taken at each time point. Wound surface area assessed by histogram planimetry (11), as well as wound infection rate will be assessed by a blinded

physician at each follow up visit. Wound area tracing by histogram planimetry will be conducted exclusively on the pictures. No tracings will be put in contact with the patients' wounds. 4D multidimensional VAS by a blinded physician and patient "scar satisfaction VAS" will be recorded at the 3 and 6 months. Patient "pain perception VAS" will be recorded at each follow up visit. Patient and physician will record any side effects occurring during the study period. Total costs in USD will also be assessed in both groups. Patients with any missing data will be asked to if they have been applying the Timolol or the Vaseline regularly, the duration of their compliance, their overall satisfaction with the wound healing process, the worst pain that they can recall and when was it after the surgery, and any other comments or concerns, including any side-effects or difficulties during the study period that they may want to share with us.

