### **Biostatistical Analysis**

To detect a 25% difference in time to improvement in each treatment arm with an 80% power, a total of 38 subjects will be enrolled in both the treatment and SOC groups (alpha level=0.05). Total subject enrollment will be 88 to adjust for subjects lost to attrition. This was calculated by considering the percentage of patients that would be healed by 30 days. In the timolol group, we estimate 85% and in the control group we estimate 60%. The Mohs and Dermatologic Surgery Center has 3 surgeons who use second intention healing on approximately 505 cases per year (~42 cases per month). If 50% of subjects agree to participate, enrollment will be complete within approximately 5 months.

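### No deciding test, hierarchy or multiplicity rule covers the several efficacy aims, so one alpha of 0.05 does not bound the chance of a false efficacy claim

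*Combined protocol and SAP*

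**What the plan says.** The opening sentence of Specific Aims makes two efficacy claims, healing and cosmesis: "To assess in a randomized fashion the efficacy and safety of topically applied 0.25% timolol gel in promoting wound healing and improve scar cosmesis". Five numbered aims follow without ranking. Aim 1 is reduction in wound surface area. Aim 2 is "Evaluating cosmetic outcomes of surgical wounds in terms of blinded physician (4D multidimensional VAS) and patient (Visual Analogue Scale, VAS) assessment at 3 and 6" (times counted in months). Aim 3 is patient-rated pain. Aims 4 and 5 are side effects and costs.

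The follow-up text (Study Procedures, after the SOC group regimen) sets five visits: days 7, 15 and 30, and months 3 and 6. Wound area is assessed at each visit by a blinded physician. "Patient 'pain perception VAS' will be recorded at each follow up visit". The two scar scales are recorded at months 3 and 6.

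Biostatistical Analysis gives one "alpha level=0.05". It opens with "To detect a 25% difference in time to improvement in each treatment arm with an 80% power" and then explains: "This was calculated by considering the percentage of patients that would be healed by 30 days". The planning rates follow: "In the timolol group, we estimate 85% and in the control group we estimate 60"%. It names no primary endpoint, no test for any endpoint, no sidedness, no order of testing, no division of alpha and no exploratory label. No other section supplies them.

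**The concern.** A stated alpha of 0.05 protects the trial's conclusion only if the reader knows which test carries that conclusion. Here at least five efficacy endpoints are available: wound area, physician scar rating, patient scar rating, pain and day-30 healing. Four of them are measured more than once. Because no analysis is specified, nothing prevents a nominal p<0.05 on one scale at one visit from being presented as evidence that timolol gel works.

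The endpoints can also disagree. Closure might be faster at day 30 with no scar difference at 6 months, or one rater's scale might differ at 3 months only. The plan does not say which result would decide. This matters most for pain and scar satisfaction, which are rated by patients who apply either the gel or Vaseline themselves. The plan describes only the physician assessor as blinded.

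**Working it through.** **1. The plan's own figure.** Inputs from Biostatistical Analysis: 85% v 60% healed by day 30, power 80%, alpha 0.05, 38 subjects, 88 enrolled in total. I read 38 as per arm, because 2 × 38 = 76 and 88 allows for attrition. Equal allocation is assumed.

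Formula: n per arm = [z_a √(2p(1−p)) + z_b √(p1(1−p1) + p2(1−p2))]² / (p1−p2)², with p = (0.85 + 0.60)/2 = 0.725, so 2p(1−p) = 0.39875. The second variance term is 0.1275 + 0.24 = 0.3675, and z_b = 0.842.

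- One-sided 0.05 (z_a = 1.645): n = 38.4, rounded up to 39. The arcsine version gives 37.5, rounded up to 38.
- Two-sided 0.05 (z_a = 1.960): n = 48.9, rounded up to 49.

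So 38 fits a one-sided test. At 38 per arm, power is 80% one-sided and 69% two-sided. At 44 per arm with no losses, two-sided power is 76%. The calculation covers one comparison, day-30 healing.

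**2. Count of possible contrasts.** Wound area at 5 visits, pain at 5 visits, and 2 scar scales × 2 visits = 4 (counting the 4D VAS as one score) make 14. Day-30 healing makes 15. With one test per endpoint the count is 5: wound area, physician scar, patient scar, pain and day-30 healing. Infection, side effects and cost are left out of both counts.

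**3. Chance of at least one false positive.** This assumes no true difference on any endpoint and each test at two-sided 0.05. If the tests are independent, the rate is 1 − 0.95^k in either direction and 1 − 0.975^k in timolol's favour:

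- k = 5: 1 − 0.95^5 = 0.226; 1 − 0.975^5 = 0.119.
- k = 15: 1 − 0.95^15 = 0.537; 1 − 0.975^15 = 0.316.

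For correlated tests I took normal test statistics with a common correlation rho and integrated numerically. The documents give no correlations, so rho is an assumption.

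| Tests | rho | Either direction | Favouring timolol |
|---|---|---|---|
| 5 | 0 | 0.226 | 0.119 |
| 5 | 0.5 | 0.183 | 0.091 |
| 5 | 0.9 | 0.102 | 0.051 |
| 15 | 0 | 0.537 | 0.316 |
| 15 | 0.5 | 0.361 | 0.181 |
| 15 | 0.9 | 0.144 | 0.072 |

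The reference values for one named two-sided test are 0.05 and 0.025.

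**4. Sidedness.** If every test were one-sided at 0.05, as the sample size suggests, the rate favouring timolol would be about 9–23% for 5 tests and 13–54% for 15, over the same range of rho. The reference is then 0.05.

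**The case against.** The strongest reply is that a lead endpoint is implied. The trial is sized on healing by 30 days, and a reader could take that as primary. This has some force and is why the fix builds on that endpoint. But the same paragraph speaks of time to improvement, Aim 1 is area reduction, and none of the three is labelled primary. Even if day-30 healing were accepted, the status of the scar and pain claims would stay open.

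A second reply is that the visit-by-visit tests are not in the plan. That is correct: the documents say what is recorded at each visit, not that each visit is tested. The count of 15 may also be generous. Aim 3 concerns discomfort while the wound heals, and with 60–85% expected to be healed by day 30, wound area and pain at months 3 and 6 may carry little information. Dropping those four from the 14 leaves 10 contrasts, with 0.287 in either direction and 0.144 favouring timolol at rho 0.5. The 15-test figures are therefore conditional, and the five-test figures are the more cautious basis.

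A reader might go further, take 14 tests at correlation 0.5, and conclude that the chance of a false finding that timolol works is about 35%. The documents do not support this. The 0.348 obtained that way counts errors in either direction, including results against timolol; the favourable share is 0.174. The correlation is assumed, and so is the number of tests.

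Finally, the blinded physician rates wound area and the 4D VAS, which are 5 + 2 = 7 of the 14 contrasts. That limits assessment bias on those measures but does not limit multiplicity.

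**Conclusion.** The point holds as a gap in specification: several efficacy endpoints, one alpha, and no rule for which result decides. The size is a range. With one two-sided test per endpoint, the chance of a false positive is about 10–23% in either direction and 5–12% favouring timolol, which is 2 to nearly 5 times the single-test values of 5% and 2.5%. If all 15 comparisons were tested, the ranges are about 14–54% and 7–32%. These rest on an assumed common correlation from 0.9 down to 0, no true effect on any endpoint, and two-sided 0.05 per test.

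Every scenario calculated exceeds the error rate of a single deciding test, so the conclusion does not depend on any one correlation or count. The documents do not show that the trial will run 15 tests or that it has any particular family-wise error rate. They leave both open.

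**What to change.** Add a paragraph to Biostatistical Analysis that does the following.

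- Name one deciding test: the proportion of wounds completely healed at day 30, timolol v SOC. State the test, its alpha and its sidedness, and define healed. This is the only contrast with planning rates.
- Then test the key secondary endpoints in fixed order at the same alpha, stopping at the first non-significant result: (1) wound surface area reduction as one overall comparison, which keeps a confirmatory place for Aim 1; (2) blinded physician 4D VAS at 6 months; (3) patient scar-satisfaction VAS at 6 months.
- Analyse pain as one overall between-arm comparison across visits.
- Label pain, wound area at individual visits, 3-month scar ratings, infection, side effects and cost as exploratory or descriptive. Report them with confidence intervals and without efficacy claims.
- Make the stated power agree with the chosen sidedness.

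Naming and ordering the tests needs no new data, visits or patients. There are two real costs. A scar claim becomes possible only if the earlier tests succeed. The gate is also not strong if the test is two-sided: 38 per arm then gives about 69% power, and 80% would need 49 evaluable per arm (98 in total, against 88 planned for enrolment). The sponsor should either state and justify a one-sided test at 0.05, or state the lower power or a larger sample.

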## **Subject Selection**

Any subjects who are interested in participating in the study will be initially approached by either a treating physician other than the PI or co-investigator to discuss treatment. All patients  $\geq 18$  years of age of either gender and any racial or ethnic background evaluated at the Mohs and Dermatologic Surgery Center who need to undergo a surgical intervention including a reconstructive phase will be eligible for participation in this study. The treating physician (which could include the PI if she is treating the patient) will approach the potential subject and will inform patients about the study during their initial consultation at the Mohs and Dermatologic Surgery Center, Dana-Farber/Brigham and Women's Cancer Center at Faulkner Hospital. If a subject indicates they would possibly be interested or would like more information, then another member of the research team will go in to privately discuss the possibility of participating. The team member will assure patients they will receive the same quality of care either way, and that their decision not to participate will in no way affect the care they receive. The patients will be encouraged to make further inquiries about the study if they are interested. Informed consent will be obtained prior to initiating the treatment. If patients are interested in taking part in the study, the investigator will approach them in private to review the consent form and address any study-related questions.

Subjects will be included for the followings reasons:

1. Age greater than 18 years
2. Open surgical wound  $\leq 1.5$ cm
3. No hypersensitivity with use of 0.25% timolol gel

Subjects will be excluded for the following reasons:

1. Age less than 18 years of age
2. Open surgical wound >1.5cm
3. Pregnant women
4. Known bradycardia
5. Use of systemic retinoids within 1 month
6. Any hypersensitivity with use of 0.25% timolol gel

## **Subject Enrollment**

The principal investigator or a co-investigator will inform patients about the study during their initial consultation at the Mohs and Dermatologic Surgery Center, Dana-Farber/Brigham and Women's Cancer Center at Faulkner Hospital. The patients will be encouraged to make further inquiries about the study if they are interested. Informed consent will be obtained prior to initiating the treatment. If a subject indicates they would possibly be interested or would like more information, then another member of the research team will go in to privately discuss the possibility of participating. The team member will assure patients they will receive the same quality of care either way, and that their decision not to participate will in no way affect the care they receive.

## **Study Procedures**

The study protocol will begin immediately post-surgery. Eligible subjects will be assigned by computer-based randomization to case (0.25% timolol gel) or control (SOC) group and treated as follows:

### Case group:

- 1) Timolol 0.25% gel will be applied to wound bed immediately after surgery before dressing is applied
- 2) Starting the day after surgery: each day, the patient will cleanse the surgical site, apply 0.25% topical timolol gel (1 drop = 0.1ml for each cm^2 of wound area), and re-cover wound with clean dressing
- 3) This daily routine continues for 12 weeks' post-surgery (even if the surgical defect has completely healed in the interim)

### SOC group:

- 1) Vaseline will be applied to wound bed immediately after surgery before dressing is applied
- 2) Starting the day after surgery: each day, the patient will cleanse the surgical site, apply Vaseline, and re-cover wound with clean dressing
- 3) This daily routine continues for 12 weeks' post-surgery (even if the surgical defect has completely healed in the interim)

Patients will be followed up at 7, 15, and 30 days' post-surgery and then at 3 and 6 months. Standardized pictures will be taken at each time point. Wound surface area assessed by histogram planimetry (11), as well as wound infection rate will be assessed by a blinded

physician at each follow up visit. Wound area tracing by histogram planimetry will be conducted exclusively on the pictures. No tracings will be put in contact with the patients' wounds. 4D multidimensional VAS by a blinded physician and patient "scar satisfaction VAS" will be recorded at the 3 and 6 months. Patient "pain perception VAS" will be recorded at each follow up visit. Patient and physician will record any side effects occurring during the study period. Total costs in USD will also be assessed in both groups. Patients with any missing data will be asked to if they have been applying the Timolol or the Vaseline regularly, the duration of their compliance, their overall satisfaction with the wound healing process, the worst pain that they can recall and when was it after the surgery, and any other comments or concerns, including any side-effects or difficulties during the study period that they may want to share with us.

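### Aim 1 is wound-area reduction, but no day-0 photograph or planimetry is explicitly scheduled, so the reduction has no defined starting area

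*Combined protocol and SAP*

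**What the plan says.** Item 1 of Specific Aims evaluates healing "in terms of wound surface area reduction of open surgical wound".

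The measurement schedule is in Study Procedures, in the follow-up text under the SOC group heading, which covers both arms:

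- Visits: "Patients will be followed up at 7, 15, and 30 days' post-surgery and then at 3 and 6 months".
- Photographs, in the next sentence: "Standardized pictures will be taken at each time point".
- Area and infection: assessed by a blinded "physician at each follow up visit".
- Source of the area: "Wound area tracing by histogram planimetry will be conducted exclusively on the pictures".

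For the day of surgery, each arm has one step. In the Case group it is "Timolol 0.25% gel will be applied to wound bed immediately after surgery before dressing is applied"; in the SOC group it is "Vaseline will be applied to wound bed immediately after surgery before dressing is applied". Neither mentions a photograph or a measurement.

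Biostatistical Analysis bases the sample size on the percentage healed by 30 days (85% against 60%). It gives no reference area for the reduction, no analysis model and no baseline covariate.

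**The concern.** A reduction needs a starting value. If area comes only from pictures, and the listed pictures begin at day 7, the earliest area is recorded after about a week of randomised treatment. It is then a post-randomisation value and cannot serve as a baseline.

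Without a day-0 area the analyst could fall back on one of two options:

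- Take day 7 as the reference. Any first-week treatment effect then becomes part of the reference, and the comparison no longer answers Aim 1.
- Compare raw areas. This is valid under randomisation, but it measures something other than reduction, and it gives up the precision that a baseline area would bring.

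A day-0 picture that was not taken cannot be recovered afterwards, so the loss is permanent for each patient enrolled without one.

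**Working it through.** **1. The schedule.** Put together, the sentences give: area requires a picture; pictures are taken at the listed time points; the list starts at day 7; the day-of-surgery steps contain only product and dressing. The first planimetric area is therefore at day 7, and percent reduction from the original wound, 1 − A(t)/A(0), has no A(0).

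**2. The plan's own figure does not depend on this.** Inputs from Biostatistical Analysis: 85% against 60% healed by day 30, alpha 0.05, power 80%, and 38 subjects, read here as per arm. The usual formula is n = [z(α)√(2p̄q̄) + z(β)√(p₁q₁ + p₂q₂)]²/δ², with p̄ = 0.725 and δ = 0.25.

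- One-sided: (1.645 × 0.631 + 0.842 × 0.606)²/0.0625 = 38.4, so 39 per arm, close to the stated 38.
- Two-sided: (1.960 × 0.631 + 0.842 × 0.606)²/0.0625 = 48.9, so 49 per arm.

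The stated 38 thus matches a one-sided test; the sidedness is not given and is a separate matter. No baseline area enters the formula, and adding a day-0 picture leaves the number unchanged.

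**3. Day 7 as the reference.** The day-7-referenced reduction is 1 − (fraction remaining at t)/(fraction remaining at day 7). All values here are assumed.

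- *Shrinks.* Timolol 40% closed at day 7 and 80% at day 30; control 20% and 70%. True difference: 80 − 70 = 10 points. From day 7: 1 − 0.20/0.60 = 66.7% and 1 − 0.30/0.80 = 62.5%, a difference of 4.2 points.
- *Vanishes.* Same day-30 values, but 50% and 25% closed at day 7: 1 − 0.20/0.50 = 60% and 1 − 0.30/0.75 = 60%, a difference of 0.
- *Grows.* One wound per arm closing at a constant radial rate, in 18 days (timolol) or 26 days (control). At day 15 the fractions remaining are (1 − 15/18)² = 0.028 and (1 − 15/26)² = 0.179, so the true reductions are 97.2% and 82.1%, a difference of 15.1 points. At day 7 the fractions remaining are (1 − 7/18)² = 0.373 and (1 − 7/26)² = 0.534. From day 7 the reductions are 92.6% and 66.5%, a difference of 26.1 points.

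**4. Chance imbalance in starting area.** Eligibility (Subject Selection) sets an upper limit of 1.5 cm and no lower limit. Assume circular wounds with diameters uniform between a lower limit L and 1.5 cm, and 38 per arm. Area is proportional to d², so CV = √(E[d⁴] − E[d²]²)/E[d²], and the 95% range of the between-arm difference, relative to the mean, is ±1.96 × CV × √(2/38).

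- L = 0.5 cm: E[d²] = 1.083, E[d⁴] = 1.5125, CV = 54%, range ±24%. Areas run from 0.20 to 1.77 cm², about 9-fold.
- L = 1.0 cm: E[d²] = 1.583, E[d⁴] = 2.6375, CV = 23%, range ±10%.

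**5. Precision forgone.** For a continuous area outcome with correlation ρ to day-0 area, adjustment multiplies the variance by 1 − ρ². With assumed ρ of 0.3, 0.5 or 0.7 this is 0.91, 0.75 or 0.51, so 38 adjusted patients per arm act like about 42, 51 or 75 unadjusted.

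**The case against.** The strongest reply is that silence is being read as absence. The photograph sentence refers to time points, while planimetry is tied to follow-up visits, and Study Procedures says that the protocol starts immediately after surgery. Surgery could be meant as a time point. This stands as an ambiguity. But the sentence directly follows a list that begins at day 7, and even on the generous reading nothing places the picture before the first application or schedules a planimetry reading of it.

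Four stronger conclusions that a reader might infer are not supported:

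- *That no adjustment for starting size is possible.* The 1.5 cm limit means that a linear size must be judged for every patient, and the Case group's gel amount per cm² implies some estimate of area in that arm. Neither is described as a recorded measurement, and neither is planimetric area. A recorded diameter could still be a crude covariate, though it could not supply the denominator for Aim 1.
- *That the powered comparison fails.* Healed by day 30 can be determined without a baseline area, and the document does not label area reduction as the primary endpoint.
- *That raw-area comparisons would be biased.* Assignment is randomised. Chance imbalance is already reflected in the standard error, and the type I error stays nominal.
- *That the trial intends day 7 as baseline.* No section says so; step 3 of the working shows only what would follow if it were used.

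The illustrations also rest on assumed inputs. In particular, healing at exactly 18 and 26 days would mean every wound healed by day 30, which does not match the plan's 85% and 60%. Those times show the direction of a possible distortion, not its expected size.

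**Conclusion.** The concern holds in this form: the first-listed aim is a reduction in area, no section explicitly schedules a day-0 photograph or planimetry, and on the plain reading the planimetric reduction from the original wound cannot be computed. A day-7 reference would not repair this, because it can shrink, remove or enlarge the treatment difference, and the data would not show which had happened.

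For healed by day 30 and for raw areas, the cost is limited to precision and protection against chance imbalance. Under the stated assumptions that imbalance has a 95% range of about ±10% to ±24% of the mean starting area. The conclusion about Aim 1 rests on the wording of the schedule and not on these figures.

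This is more than a missing detail, because the day-0 value cannot be obtained later.

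**What to change.** Amend the document in three places:

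- **Study Procedures, both arms:** add a standardized, scaled photograph on day 0, after surgery and before the first timolol or Vaseline application, with area read by the same blinded histogram planimetry as at later visits.
- **Specific Aims, item 1:** define the outcome as percent reduction from this day-0 area.
- **Biostatistical Analysis:** pre-specify day-0 area as a covariate in the wound-healing analyses.

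If a surgery-day picture was always intended, the first change merely states it and fixes its timing. The cost is one photograph while the patient is already in clinic, one planimetry reading per patient, and a short amendment. The stated sample size does not change.

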### **Risks and Discomforts**

The risks and discomforts of the topical application of 0.25% timolol gel include erythema, itching, irritant or allergic contact dermatitis in case of patient sensitization. Other discomforts and risks, including pain and infection, are implied in the surgical procedure patients have undergone (in both groups).

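### Local side effects are recorded without blinding or a common list, so the Aim 4 comparison is at risk of recording that differs by arm, in an uncertain direction

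*Combined protocol and SAP*

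**What the plan says.** Specific Aims, item 4, sets a between-arm comparison: "Determining the side effects associated to 0.25% topical timolol versus SOC". The rule that feeds it is one sentence in the follow-up text under SOC group: "Patient and physician will record any side effects occurring during the study period". There is no definition of a side effect, list of reactions to look for, grading scale, fixed question or rule on attribution.

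The same text names a blinded physician for wound area and infection at each follow-up visit, and for the scar rating: "4D multidimensional VAS by a blinded physician". The side-effect sentence has no such word.

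On treatment, Study Procedures says "Eligible subjects will be assigned by computer-based randomization to case (0.25% timolol gel) or control (SOC) group". In the timolol arm, "the patient will cleanse the surgical site, apply 0.25% topical timolol gel"; in the control arm, "the patient will cleanse the surgical site, apply Vaseline, and re-cover wound with clean dressing". No matched vehicle or masking of patients is described.

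Risks and Discomforts begins: "The risks and discomforts of the topical application of 0.25% timolol gel include erythema, itching", and goes on to contact dermatitis. It lists no product reaction for Vaseline. Pain and infection are put down to the surgery, in both groups.

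**The concern.** Redness and itching are signs that an open wound can show while it heals, with or without a drug. Whether such a sign is written down as a side effect depends on who is looking and what that person expects. Here the patient effectively knows the product, the physician may know it, and the protocol associates these signs with one product only. The same sign could be noted in one arm and passed over as ordinary healing in the other.

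At stake is the tolerability half of the trial's efficacy-and-safety question. If recording differs by arm, a difference in reported reactions cannot be separated from a difference in reporting, and a true difference could equally be hidden. No later analysis can reliably undo this, because the unrecorded events leave no trace in the data.

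**Working it through.** The documents give no side-effect rate and no side-effect analysis, so there is no figure to reproduce. The check is a side-by-side reading followed by an illustration.

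**1. Who records what**

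| Outcome | Recorder and timing | Blinding stated | Needs to be called a side effect |
|---|---|---|---|
| Wound area | Physician, from photographs, each visit | Yes | No |
| Infection | Physician, each visit | Yes | No |
| Scar, 4D VAS | Physician, 3 and 6 months | Yes | No |
| Scar satisfaction VAS | Patient, 3 and 6 months | No | No |
| Pain VAS | Patient, each visit | No | No |
| Side effects | Patient and physician, no fixed times | No | Yes, and the term is undefined |

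The side-effect row is the only one with neither stated blinding nor a fixed instrument and timing.

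**2. Do patients know their arm?** This is a strong inference, not an explicit statement. They apply a drop-dosed gel or Vaseline themselves, no matched vehicle is described, and patients with missing data are asked about their use of Timolol or Vaseline by name.

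**3. Does anything else capture local reactions neutrally?** The adverse-event wording in Monitoring and Quality Assurance governs submission of unanticipated problems to the IRB. Erythema and itching are anticipated in Risks and Discomforts, so that wording does not supply data for Aim 4. The open question about side effects or difficulties goes only to patients with missing data.

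**4. Illustration of size.** All rates are assumed; none comes from the documents.

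- p = true rate of a local reaction, the same in both arms: 10%, 20% or 30%.
- s(T), s(C) = share of true reactions recorded with timolol and with control.
- Recorded rate = p × s. Apparent risk ratio = s(T) / s(C), because p cancels.

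With s(T) = 0.90 and s(C) = 0.60:

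- p = 10%: 0.10 × 0.90 = 9% versus 0.10 × 0.60 = 6%
- p = 20%: 18% versus 12%
- p = 30%: 27% versus 18%
- Apparent risk ratio = 0.90 / 0.60 = 1.5 in each case, with a true ratio of 1.

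Reversed (0.60 with timolol, 0.90 with control): 0.60 / 0.90 = 0.67. Equal recording gives 1.0. Holding s(T) at 0.90 and varying s(C) from 0.50 to 0.80 gives 1.8 down to about 1.1.

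**5. What a test would show.** Take 88 / 2 = 44 per arm (equal allocation and no losses assumed) and a two-sided Fisher exact test at 0.05. Exact enumeration gives these chances of a false finding of more reactions on timolol:

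| True rate | 90% vs 60% recorded | 80% recorded in both |
|---|---|---|
| 10% | 2.5% | 0.7% |
| 20% | 7.1% | 1.25% |
| 30% | 11.0% | 1.3% |

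If recording is reversed, the left-hand chances apply to a false finding of fewer reactions on timolol. In patients, the 20% row is a gap of (0.18 − 0.12) × 44 = 2.6 per arm: small in number, but a large part of a comparison based on about 8 versus 5 events.

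**The case against.** A reader might infer that the comparison is biased toward finding reactions on timolol. The documents do not support a fixed direction. Listing these reactions for timolol only makes an excess there plausible. Against that, Background and Significance presents the gel as safe and painless, and Potential Benefits expects faster healing, less pain and more satisfied patients. Recorders who share those expectations could under-record on timolol. This objection stands.

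A reader might also infer that an event is recorded only if someone judges the treatment to have caused it. The text asks for any side effects and states no causality judgement. The undefined term permits that reading but does not establish it. Likewise, the recording physician is not said to be unblinded and might be the blinded assessor; the text leaves this open.

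The scope is limited too. Pain is collected from every patient at each visit, and infection by a blinded physician, in both arms and without attribution. Pain remains an unblinded patient report, as does scar satisfaction, so open-label reporting is not peculiar to side effects. What stays exposed is erythema, itching and dermatitis.

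Finally, the plan states no test of side effects, so no planned result is shown to change. That is true, but Aim 4 is still a comparison, and a descriptive table is distorted by unequal recording just as a test is.

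**Conclusion.** The point holds as a risk of differential recording of local reactions, not as a demonstrated bias of known sign. It rests on two things in the text (no stated blinding and no common list or definition for side effects) and on the strong inference that patients know which product they apply.

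The size cannot be estimated from the documents. Under assumed recording of 90% versus 60% the spurious risk ratio is 1.5, and 0.67 if reversed; with equal recording there is no distortion. The conclusion should not be extended to harms in general, since pain and infection have their own capture in both arms, nor to wound area or the physician's scar rating, which are assigned to a blinded physician.

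The change is worth making because the blinded assessor and the visits already exist.

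**What to change.** In the follow-up text under SOC group in Study Procedures:

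- Have the blinded physician who already assesses infection record presence and severity of erythema and dermatitis on a fixed list at each visit, in both arms, regardless of suspected cause. Ask patients not to reveal their treatment to this physician.
- At each visit, ask patients in both arms one identically worded question about itching and about any reaction since the last visit.
- Record all events regardless of attribution, and keep between-visit reports in the Aim 4 comparison. There is no visit between day 30 and 3 months while daily application runs to 12 weeks, so a reaction that came and went in that interval would be lost if only visit-day findings counted.
- Show blinded-physician findings and open-label patient reports separately by arm.

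Cost: a short checklist and one question at visits already planned. Recorded rates will rise in both arms because background signs of healing are counted. Itching remains an unblinded patient report and should be stated as a limitation. The blind for erythema and dermatitis will be only as good as the one already relied on for infection.
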